6.2.2 Secondary efficacy variables

6.2.2.1 Menstrual blood loss

Subjects in the HMB subgroup are requested to collect their used sanitary products during four periods of 30 days each, as described in Integrated Protocol Section 9.1 and Integrated Protocol Table 9–2, i.e. for the following study days:

- beginning of Year 6, i.e. 30 days after baseline visit = study days 2-31
- end of Year 6, i.e. 30 days prior to Visit 4 (-14 days) = study days 322-351
- end of Year 7, i.e. 30 days prior to Visit 6 (-14 days) = study days 687-716
- end of Year 8, i.e. 30 days prior to Visit 8 (-14 days) = study days 1052-1081

MBL data will be available per HMB subject per collection period per day per sanitary product. MBL data from sanitary products collected during these planned 30-day collection periods will be included in the statistical analysis; potential additional MBL data from sanitary products collected outside these planned 30-day collection periods will be excluded from the statistical analysis.

Since MBL is related to the bleeding intensity, missing MBL data during the planned 30-day collection periods will be imputed depending on the subject's daily bleeding intensity recorded in the eDiary, as described in Section 4.5.

The cumulative volume of MBL will be calculated only if a day-wise cumulative MBL (original or imputed value, as described in Section 4.5 and Table 4–1) is available for each day in the planned 30-day collection period (or until the day of premature discontinuation). Otherwise, the collection period will be considered invalid and the cumulative volume of MBL will not be calculated.

If there are less than 20 solid observations in a planned 30-day collection period (“solid” as defined in Section 4.5 and Table 4–1), the collection period will be considered invalid and the cumulative volume of MBL will not be calculated. This rule also applies to HMB subjects who discontinued prematurely during a 30-day collection period, i.e. if there are less than 20 solid observations before the subject discontinued prematurely during a 30-day collection period, the collection period will be considered invalid and the cumulative volume of MBL will not be calculated.

The cumulative volume of MBL will be calculated per HMB subject per analysis period as the sum of MBL values, adjusted for the length of the analysis period (in case of early and/or late collection without gap, and/or in case of premature discontinuation). That means the sum of MBL values will be multiplied by {length of analysis period in units of days divided by 30 days}.

The cumulative volume of MBL at beginning of Year 6, end of Year 6, end of Year 7, and end of Year 8 of Mirena treatment will be presented by descriptive statistics. Furthermore, change from baseline (=beginning of Year 6) will be presented.

The basis for this analysis is the data on MBL assessed by the alkaline hematin method (see Integrated Protocol Section 9.4.2). If a women has sent in no sanitary products and has documented in the eDiary (see Integrated Protocol Section 9.7.1) that no bleeding occurred during one of the considered 30-day time periods for collection of sanitary protection, the MBL will be assumed to be zero in that time period.

This analysis will be conducted in the FAS in the HMB subgroup, i.e. women who had Mirena inserted for both contraception and HMB.

Sensitivity analysis approach #1 of MBL:

As described in Section 4.5, there might be cases when the MBL value remains missing. If such cases occur, a sensitivity analysis will be performed using (imputed) MBL values based on the extended imputation rules given in Section 4.5.

The cumulative volume of MBL will be calculated and summarized similarly as in the above primary analysis approach for MBL.

[figure not shown]

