Subjects in the HMB subgroup (i.e. all women who had the Mirena inserted for contraception and heavy menstrual bleeding) will collect their used sanitary products (provided by sponsor) during 4 periods of 30 days as shown in [Table 9–2](#). All used sanitary products have to be returned to the study site as instructed in [Section 9.4.2](#) and displayed in [Table 9–2](#).

For subjects who have the Mirena inserted for contraception only: if bleeding irregularities develop during prolonged treatment, appropriate diagnostic measures should be taken by the investigator to rule out endometrial pathology.

Table 9–2 Schedule of activities needed for the MBL evaluations – amended

HMB subgroup only – additional activities for baseline (BL) visit and treatment period. For all other activities and evaluations, see [Table 9–1](#).

Period	Screening	Treatment Period (Mirena years 6 thru 8)										
		30 days after baseline visit, Study Days 2 to 31 (inclusive)		Study Days 322 to 351 (inclusive) before Visit 4			Study Days 687 to 716 (inclusive) before Visit 6			Study Days 1052 to 1081 (inclusive) before EOT visit		
Collection time		Return	Return	Visit 3	Return	Visit 4	Visit 5	Return	Visit 6	Visit 7	Return	EOT Visit 8
Visit / visit number	Baseline (BL) Visit 2											
Dispense alkaline hematin kit	X			X			X			X		
Collection of used sanitary products		→	→		→	→		→	→		→	→
Return of used sanitary products ^a		X	X		X	X		X	X		X	X

Study Day 1 = Day of the baseline visit (Visit 2)

a Used sanitary products should not be kept at home longer than 14 days. Return required only if sanitary products have been used in the time periods indicated.

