9.4.2 Assessment of menstrual blood loss (MBL) by alkaline hematin method

For the subjects in the HMB subgroup, the MBL will be assessed 4 times during the study. The 30-day assessment periods are scheduled as the first 30 days of the treatment period (starting at baseline visit, Visit 2) and for the 30 days before visits 4, 6 and 8. The subjects in this subgroup will be required to use the selected types of sanitary products (towels, tampons and panty liners) provided by the sponsor and to collect their used sanitary products during these 4 periods. Subjects will return the used products to the study site at two week intervals, and all used sanitary products will be sent to the central laboratory for analysis. Please see [Table 9–2](#) for timing of the 4 periods and the required visits.

Details of the alkaline hematin method are given in the lab manual.

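### SAP 6.2.2.1 excludes menstrual blood loss collected outside fixed study days, then length-adjusts for early or late collection, with a factor that runs the wrong way

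*SAP*

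**What the plan says.** SAP 6.2.2.1 fixes the windows by study day: 2-31, 322-351, 687-716 and 1052-1081. For example: "end of Year 6, i.e. 30 days prior to Visit 4 (-14 days) = study days 322-351". SAP 4.5 and Protocol Table 9-2 give the same days.

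Three rules then follow in SAP 6.2.2.1:

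- Products "collected outside these planned 30-day collection periods will be excluded from the statistical analysis".
- A cumulative volume is computed only if a day-wise value, original or imputed, "is available for each day in the planned 30-day collection period (or until the day of premature discontinuation"). A window with fewer than 20 solid observations is invalid.
- The volume is the sum of the MBL values, "adjusted for the length of the analysis period (in case of early and/or late collection without gap, and/or in case of premature discontinuation"). The adjustment multiplies the sum by the analysis-period length in days over 30.

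Protocol 9.4.2 describes the later collections as "for the 30 days before visits 4, 6 and 8" and starts the first at the baseline visit. It then sends the reader to Table 9-2 for timing.

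**The concern.** Under the exclusion and completeness rules, the analysis period is 30 days for every woman who does not discontinue inside a window. Early or late collection cannot lengthen it, because the extra products are dropped. It cannot shorten it either, because every planned day needs a value. The early/late trigger therefore has no case to act on, unless it is read as letting the excluded days back in. A programmer has to choose, and the visible text gives no basis for the choice.

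The factor is a second problem. To express a volume per 30 days, a sum over a short period must be scaled up. Length over 30 scales it down.

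The stakes lie in SAP 6.2.2.2 and Protocol 10.3.2.2. A woman with 80 mL or more in an assessed window counts as a clinical change. Success requires fewer than 20% of the HMB subgroup to have a change, and a 95% Clopper-Pearson upper limit of at most 35%. The target for that subgroup is 36 women.

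**Working it through.** **1. The planned windows reproduce.** Nominal visit days are 365, 730 and 1095 (SAP 4.7). Window end = visit day − 14 = 351, 716, 1081. Window start = end − 29 = 322, 687, 1052. All three match the SAP, so the fixed windows themselves are coherent.

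**2. When can the length differ from 30?** Excluding outside products caps the length at 30. Requiring a value for each planned day keeps it at 30, except after premature discontinuation. Only discontinuation is left as a trigger.

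**3. Effect if the early/late trigger is applied anyway.** Assumed woman: 70 mL inside days 322-351, and gap-free dry collection on to day 364. Length = 364 − 322 + 1 = 43.

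- Exclusion rule: 70 mL, below 80.
- Adjustment as written: 70 × 43/30 = 100.3 mL, at or above 80.

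At this length, any in-window sum from 80 × 30/43 = 55.8 mL to just under 80 mL changes class in the same way.

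**4. Correcting the factor alone does not remove the conflict.** Take 90 mL in the window with the same dry collection to day 364. The exclusion rule gives 90 mL and the written factor gives 90 × 43/30 = 129 mL, so both count her as a change. If the factor were turned round but the early/late trigger kept, the result would be 90 × 30/43 = 62.8 mL, which is no change. Both edits are needed.

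**5. The factor for discontinuers.** Assumed woman: 60 mL over 20 days, then discontinuation.

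- As written: 60 × 20/30 = 40 mL.
- Per 30 days: 60 × 30/20 = 90 mL.

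The 20-observation minimum restricts the length L to 20-29 days. The two versions disagree about 80 mL for sums from 80 × L/30 up to just under 80 × 30/L:

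| L (days) | Lowest sum affected | Sums affected stay below |
|---|---|---|
| 20 | 53.3 mL | 120 mL |
| 29 | 77.3 mL | 82.8 mL |

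In each range the written factor puts the woman below 80 mL. SAP 4.4 does the opposite for bleeding diaries: reference length over diary length, 15 × 90/75 = 18 days.

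**6. Weight of one woman.** The upper limit is the 0.975 quantile of Beta(x + 1, n − x).

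| n | Changes | Proportion | Upper limit | Result |
|---|---|---|---|---|
| 36 | 6 | 16.7% | 32.8% | pass |
| 36 | 7 | 19.4% | 36.0% | fail |
| 30 | 5 | 16.7% | 34.7% | pass |
| 30 | 6 | 20.0% | 38.6% | fail |
| 20 | 2 | 10.0% | 31.7% | pass |
| 20 | 3 | 15.0% | 37.9% | fail |

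The 36 is the plan's target. The 30 is illustrative, and the 20 is 36 × 200/360, the completer ratio for the whole study.

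**The case against.** The strongest defence is the redaction. The data types in SAP 4.5 and its Table 4-1 are blacked out, and early or late collection without a gap may be defined there. That stands as a limit on the point. It does not dissolve it, because the exclusion in SAP 6.2.2.1 carries no exception, and any redacted definition would still have to be squared with it.

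It can also be said that length over 30 is a slip that any programmer would correct. That is plausible, but the SAP is the specification, and a silent correction would be an undocumented departure from it.

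A reader might go further and infer two rival windows, the fixed days and the 30 days before the visit actually held. On that reading, a visit on day 365 leaves only 17 collected days in the fixed window, and 17 of the 29 permitted days for Visits 4 and 6 leave fewer than 20, so many windows would be invalid. The documents do not support this. No text anchors collection to the visit actually held. Protocol 9.4.2 defers to Table 9-2, which reads "Study Days 322 to 351 (inclusive) before Visit 4". The SAP equates its visit wording with the study days, and day 351 is the earliest permitted Visit 4. Those counts assume that sites ignore the table. They also assume that uncollected days are not solid, but that definition is redacted, and the SAP imputes missing MBL from the eDiary. Protocol 9.4.2 needs alignment and nothing more.

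Finally, the documents do not say how many women collect early or late, or discontinue inside a window. The number may be small.

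**Conclusion.** The point holds for the text of SAP 6.2.2.1. The exclusion and completeness rules leave the early/late length adjustment without a function, and applying it can move a woman across 80 mL (70 against 100 mL in the example). The inverted factor is the firmer of the two errors, since it acts even when only the fixed days are used. It understates blood loss for women who discontinue inside a window (40 against 90 mL). Protocol 6.4.1 allows withdrawal when heavy bleeding returns, so these can be the women in whom an understatement matters most.

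The patient values are assumed for illustration, and the conclusion is subject to the redacted part of SAP 4.5. How many women are affected cannot be estimated from the documents. One is enough if the count sits at the boundary, 6 against 7 of 36. That justifies a correction. It does not show that the endpoint is compromised.

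**What to change.** 1. **SAP 6.2.2.1, adjustment sentence.** Strike the condition on early and/or late collection, leaving premature discontinuation as the only trigger. Every woman is then scored on the fixed study days. If the redacted text defines early/late collection, amend it to agree.
2. **Same sentence.** Write the factor as 30 divided by the length of the analysis period, and define that period as the planned days up to discontinuation.
3. **Protocol 9.4.2.** Replace the visit-based wording and the baseline-visit start with the Table 9-2 study days (2-31, 322-351, 687-716, 1052-1081). This is alignment only. Protocol 10.3.1.1.2 has the same one-day difference at baseline.
4. **Optional sensitivity analysis.** Where the fixed window is invalid, use a contiguous 30-day collection that ends on or before the visit, if there is one.

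The cost is a few lines in the SAP, one sentence in the protocol and, if wanted, one table. The downside is that off-window collections do not enter the main table. As Year 6 and Year 7 results have already been reported, the SAP's change history should state which rule and which factor were programmed for them.

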10.3.2.2 Analysis of the secondary variables

10.3.2.2.1 Menstrual blood loss

This section was changed in Amendment 1, see Section 15.1.1.10.

Menstrual blood loss (MBL) at beginning of year 6, end of year 6, end of year 7, and end of year 8 of Mirena treatment will be presented by descriptive statistics. Furthermore, change from baseline (=beginning of year 6) will be presented.

The basis for this analysis is the data on MBL assessed by the alkaline hematin method (see section 9.4.2). If a woman has documented in the eDiary (see section 9.7.1) that no bleeding occurred during one of the 30-day time periods considered for collection of sanitary products, the MBL will be assumed to be zero in that time period. The handling of partial or missing data (i.e. data on sanitary products and/or bleeding intensities) and detailed imputation rules will be described in the statistical analysis plan.

This analysis will be conducted in the FAS in the HMB subgroup, i.e. women who had Mirena inserted for both contraception and HMB.

CCI

CCI [REDACTED]

[REDACTED]

[REDACTED]

[REDACTED]

- [REDACTED]
- [REDACTED]

[REDACTED]

[REDACTED]

- [REDACTED]
- [REDACTED]

[REDACTED]

[REDACTED]

- [REDACTED]
- [REDACTED]
- [REDACTED]

[REDACTED]

[REDACTED]

- [REDACTED]
- [REDACTED]
- [REDACTED]

CCI [REDACTED]

- [REDACTED]
- [REDACTED]
- [REDACTED]
- [REDACTED]

[REDACTED]

- [REDACTED]
- [REDACTED]
- [REDACTED]
- [REDACTED]

Success will be concluded regarding this endpoint if less than 20% of the women in the HMB subgroup have a clinical change in bleeding profile regarding HMB (according to the definition above) and the upper limit of the corresponding 95% Clopper-Pearson confidence interval is equal to or less than 35%.

This analysis will be conducted in the FAS in the HMB subgroup, i.e. women who had Mirena inserted for both contraception and HMB.

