15.1.2.31 Section 10.3.2.2.2 Categorized menstrual blood loss (MBL) (<80ml / 30 days)

This section was changed as a result of Modification 15.1.1.11.

Old text:

No clinical change in bleeding profile regarding HMB will be concluded if the volume of blood loss ~~remains~~ < 80mL ~~during~~ the end of years 6, 7 and 8. Therefore, the proportion of women with ~~an MBL <80 mL / 30 days will~~ analyzed. Descriptive statistics as well as 95% Clopper-Pearson confidence intervals will be provided ~~for each of the time periods in which HMB is assessed.~~ Success will be concluded regarding this endpoint if less than 20% of the women ~~included into the study for HMB~~ have a clinical change in bleeding profile (according to the definition above).

This analysis will be conducted in the FAS in the subgroup ~~of~~ women who had Mirena inserted for HMB.

New text:

No clinical change in bleeding profile regarding HMB after Year 5 until the end of Year 6, until the end of Year 7 and until the end of Year 8, respectively, will be concluded if the volume of blood loss was < 80mL at the beginning of Year 6 and remained < 80mL at the end of Years 6, 7 and 8, respectively. Vice versa, clinical change in bleeding profile regarding HMB after Year 5 until the end of Year 6, end of Year 7 and end of Year 8, respectively, will be concluded if the volume of blood loss was \geq 80mL at the beginning of Year 6 or at end of Years 6, 7 or 8, respectively.

Therefore, the proportion of women with clinical change in bleeding profile regarding HMB will be analyzed. Descriptive statistics as well as 95% Clopper-Pearson confidence intervals will be provided.

For the analysis after 6 years, the proportion of women with clinical change in bleeding profile regarding HMB after Year 5 until the end of Year 6 will be analyzed.

For the analysis after 6 years, the following women will constitute the denominator:

- Baseline MBL >80mL/30days, or
- Baseline MBL not >80mL/30days and End of Year 6 MBL assessment available.

That means, women with Baseline MBL not >80mL/30days and MBL assessment at the end of Year 6 not available will be excluded from the denominator, as they are considered lost to follow up without preceding clinical change in bleeding profile regarding HMB.

For the analysis after 6 years, the following women will constitute the nominator:

- Baseline MBL>80mL/30days, or
- End of Year 6 MBL>80mL/30days.

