6.2.2.2 Categorized menstrual blood loss (<80 mL / 30 days)

No clinical change in bleeding profile regarding HMB after Year 5 until the end of Year 6, until the end of Year 7 and until the end of Year 8, respectively, will be concluded if the cumulative volume of MBL was < 80mL at the beginning of Year 6 and remained remains <80mL during the end of years 6, 7 and 8, respectively. Vice versa, clinical change in bleeding profile regarding HMB after Year 5 until the end of Year 6, end of Year 7 and end of Year 8, respectively, will be concluded if the volume of blood loss was ≥ 80mL at the beginning of Year 6 or at end of Years 6, 7 or 8, respectively.

Therefore, the proportion of women with clinical change in bleeding profile regarding HMB will be analyzed. Descriptive statistics as well as 95% Clopper-Pearson confidence intervals will be provided.

For the analysis after Year 6, the proportion of women with clinical change in bleeding profile regarding HMB **after Year 5 until the end of Year 6** will be analyzed.

CCI
[Redacted text block]

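### On the readable text, a blood-loss window can be declared invalid although 80 mL has already been measured in it, so a woman who meets the HMB failure threshold may not count as a failure

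*SAP*

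**What the plan says.** SAP 6.2.2.1 sets two validity conditions for each 30-day collection window in the HMB subgroup.

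- **Every day filled.** "The cumulative volume of MBL will be calculated only if a day-wise cumulative MBL", original or imputed, exists for each day of the window or up to the day of discontinuation. "Otherwise, the collection period will be considered invalid and the cumulative volume of MBL will not be calculated".
- **At least 20 solid days.** "If there are less than 20 solid observations in a planned 30-day collection period", then "the collection period will be considered invalid and the cumulative volume of MBL will not be calculated". For early leavers the SAP adds: "This rule also applies to HMB subjects who discontinued prematurely during a 30-day collection period".

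SAP 6.2.2.2 turns the volume into a binary endpoint. Clinical change "will be concluded if the volume of blood loss was ≥ 80mL at the beginning of Year 6" or at the end of a later assessed year.

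The readable counting rules are in Protocol 15.1.2.31, the Amendment 1 text for Section 10.3.2.2.2. A woman with a failure in an earlier window stays in numerator and denominator whatever follows. A woman without one, whose final assessment is not available, is "excluded from the denominator, as they are considered lost to follow up without preceding clinical change in bleeding profile regarding HMB".

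Protocol 10.3.2.2 declares success if fewer than 20% have a clinical change and "the upper limit of the corresponding 95% Clopper-Pearson confidence interval is equal to or less than 35" per cent.

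SAP 6.2.2.1 also plans a sensitivity analysis with extended imputation for values that stay missing.

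**The concern.** Daily blood loss cannot be negative. If the products analysed from part of a full window already contain 80 mL, the 30-day total is at least 80 mL whatever the missing days hold. A completeness rule makes sense for estimating a mean, or for showing that loss stayed below 80 mL. It is not needed to establish that 80 mL was exceeded.

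As printed, the rule removes the volume on which SAP 6.2.2.2 classifies the woman. If the void window is the final one, she appears to leave the denominator as a woman without preceding change, which her own measurements contradict. If it is an earlier one and the final window is valid and below 80 mL, she appears to stay in as a non-failure, because the condition of being not above 80 mL seems to include missing. Either way the proportion with clinical change is lower than the measured data support.

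The endpoint has a formal success rule and few women, so a single misplaced woman can matter. The loss could also be related to outcome. Protocol 6.4.1 lists return of heavy bleeding as a possible reason for withdrawal, and a woman who leaves before window day 20 cannot have 20 solid days.

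**Working it through.** **Inputs**

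- HMB target: 36 of 360 (SAP 3, Protocol 5). Check: 0.10 × 360 = 36. No power figure for the HMB criterion is readable.
- Achieved subgroup: described as low in SAP 7 (v2.0 entry), number not given. Assumed range 20 to 36. The lower end is 36 × 200/360 = 20, if HMB women complete at the overall target rate.
- Success: x/n < 20% and two-sided 95% Clopper-Pearson upper limit ≤ 35%, where upper limit = Beta⁻¹(0.975; x+1, n−x).
- Share of failures lost to an invalid window: not given, so varied below.

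**Largest number of failures that still passes:** 6 at n = 36, 5 at n = 30, 3 at n = 25, 2 at n = 20.

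**Effect of dropping failures from numerator and denominator**

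| All failures counted | Upper limit | Success | Dropped | Result | Upper limit | Success |
|---|---|---|---|---|---|---|
| 7/36 = 19.4% | 36.0% | no | 1 | 6/35 = 17.1% | 33.7% | yes |
| 8/36 = 22.2% | 39.2% | no | 2 | 6/34 = 17.6% | 34.5% | yes |
| 4/25 = 16.0% | 36.1% | no | 1 | 3/24 = 12.5% | 32.4% | yes |
| 3/20 = 15.0% | 37.9% | no | 1 | 2/19 = 10.5% | 33.1% | yes |

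If the void window is an earlier one and the woman is kept as a non-failure, 7/36 becomes 6/36 = 16.7%, upper limit 32.8%: also a success.

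The flip is not universal. At n = 30, 6/30 = 20.0% fails; dropping one gives 5/29, upper limit 35.8%, still a failure. Two must be dropped (4/28, 32.7%).

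**Probability of success if a share q of true failures is lost and no non-failure is.** Summing over x failures and d lost: P = Σ Bin(x; n, p) · Bin(d; x, q), over pairs where (x−d)/(n−d) meets both limits.

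| n, true rate p | q = 0 | 10% | 20% | 30% |
|---|---|---|---|---|
| 36, 20% | 40.1% | 51.6% | 61.9% | 71.1% |
| 36, 25% | 16.8% | 26.1% | 35.6% | 46.0% |
| 36, 35% | 1.3% | 3.2% | 5.9% | 10.5% |
| 25, 25% | 9.6% | 15.3% | 22.8% | 31.6% |

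This describes loss confined to failures. It is not a forecast.

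**How often early leavers could be affected.** Window days 1 to 19 in four windows are 4 × 19 = 76 of about 1095 days, or 7%. With 36 − 20 = 16 HMB discontinuers spread evenly, 16 × 76/1095 ≈ 1.1 women would leave in those days, before also requiring 80 mL already measured.

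**Shortened windows.** SAP 6.2.2.1 multiplies the sum by length/30. For 90 mL in 20 days that gives 90 × 20/30 = 60 mL, and 80 × 30/20 = 120 mL would be needed to reach 80. The proof of exceedance is therefore clean under the SAP's own formula only for full-length windows with missing days.

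**The case against.** **Windows are voided whatever their blood loss.** A reader might infer that the rule selectively deletes failures. It does not: low-loss windows with too few solid days are discarded too. Only what can be proven from a partial window is one-sided. If incompleteness is unrelated to blood loss, the printed rule is a complete-case estimate with the right expectation: (0.15 × 0.8)/0.8 = 15% at a true rate of 15% with 20% of windows invalid. This stands.

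**The remedy is itself asymmetric.** It admits incomplete windows only as failures. In the same setting the expected proportion becomes (0.12 + 0.015)/(0.80 + 0.015) = 16.6% if half of the failing invalid windows already show 80 mL, and 0.15/0.83 = 18.1% if all do. With 30% invalid and all showing 80 mL it is 0.15/0.745 = 20.1%, above the 20% limit. The arithmetic is right and the cost must be named. But the counting rules in Protocol 15.1.2.31 already have this shape: they keep known failures with later data missing and exclude incomplete non-failures.

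**Decisive text is redacted.** This covers the definition of solid and the imputation rules (SAP 4.5, Table 4–1), the SAP's numerators and denominators, and the body of Protocol 10.3.2.2.2. A rescue rule there cannot be excluded, although it would sit badly with the unconditional wording of SAP 6.2.2.1. Treating invalid as not available is an inference. SAP 6.2.2.2 also defines no change by cumulative volume but change by volume of blood loss, so the readable text does not settle whether a void window is barred from registering a change.

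**The unfillable-day condition is partly covered** by diary-based imputation and the sensitivity analysis. Nothing readable says that analysis lifts the 20-day condition.

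**Women leaving because of bleeding are visible elsewhere,** as adverse events (Protocol 9.6.1.3) and in discontinuations by reason (SAP 6.1.3.4). That does not bring them into the HMB criterion.

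**Conclusion.** The point holds in a limited form. On the readable text, a woman whose measured blood already meets the plan's own failure threshold can be left out of the success criterion or counted as a non-failure. At the boundary, one such woman is enough at n = 36, 25 and 20; at n = 30 it takes two.

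This rests on three assumptions: that an invalid window is handled as unavailable, that the redacted text holds no rescue rule, and that the Amendment 1 counting text is still in force. How often it happens cannot be computed and is probably low.

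Two stronger readings are not supported. A reader might infer that mean blood loss is biased downward, but low-loss windows are voided too and no such bias is shown. A reader might also infer a general bias toward success; that would need incompleteness related to blood loss, which is plausible for some early leavers but not demonstrated.

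Severity is minor to moderate, confidence moderate.

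**What to change.** Add to SAP 6.2.2.2: *If measured MBL (not imputed, not length-adjusted) within a planned collection window totals 80 mL or more, the woman counts as having a clinical change, in numerator and denominator, whatever the validity of that window.* Keep both validity conditions for windows below 80 mL and for the continuous summary.

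Report how many invalid windows had a measured total of 80 mL or more, and show the result under the printed rule as a sensitivity analysis. If redacted text already contains such a rule, a cross-reference in SAP 6.2.2.1 is enough. Reconcile the length/30 factor for shortened windows separately.

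The cost is one sentence and one programming condition, with no new data. The downside should be stated in the SAP: the rule is conservative, because incomplete windows enter only as failures, so the proportion may be somewhat overstated if incompleteness is unrelated to blood loss. The Year 6 and Year 7 analyses have already been reported according to SAP 6.2.1, so applying the rule to them would be post hoc and should be labelled so.
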